16.3 Analysis on Subgroups

Analysis on subgroups as defined in Section 10 will be performed for the primary and key secondary efficacy endpoints. In addition, the odds ratio and its 95% CI corresponding to the ORR of each subgroup relative to the reference subgroup will be calculated, and the p-value from Fisher's exact test will be provided to assess the association between each subgroup factor and ORR. Furthermore, to compare PFS time and OS time within each subgroup factor, the hazard ratio and its 95 % CI of each subgroup relative to the reference subgroup will be calculated using Cox proportional hazards model.

A forest plot will be created to graphically present ORR and its 95% CIs for the ITT analysis set and all the subgroups.

CCI [REDACTED]. In case of low number of subjects within a category (< 5 subjects, which is about 5% of the study population), subgroups will be pooled.

16.4 Other Endpoint Analyses

Analysis sets: ITT analysis set

16.4.1 Time to Response per RECIST 1.1

Time to response (TTR) is defined, for subjects with an objective response, as the time from the start of first study treatment to the first documentation of objective response (CR or PR) which is subsequently confirmed.

$TTR \text{ (in weeks)} = (\text{data of first objective response} - \text{date of first dose of study treatment} + 1)/7$

TTR will be summarized using simple descriptive statistics (mean, StdDev, median, min, max, Q1, Q3).

CCI [REDACTED]

CCI

CCI

CCI

CCI

CCI

16.4.6 Duration of Follow-up

Kaplan-Meier analysis will be performed to estimate median time of duration of follow-up for PFS using the censoring rules (reverse censoring indicator) as specified in Table 5.

Table 5 Reverse Censoring Rules for Duration of Follow-up

| Endpoint | Event | | Date of event / censoring | Censoring |
|-------------------------------|-------------------|-----|--|-----------|
| Duration of follow-up for PFS | First PD or Death | Yes | Time from first dose of study treatment to date of first PD or death | Yes |
| | | No | Time from first dose of study treatment to last date known to be alive | No |

Kaplan-Meier survival curves will be presented with median duration of follow-up and its two-sided 95% CI. In particular, the follow-up rate at 3, 6 and 12 months will be estimated with corresponding two-sided 95% CIs.

CCI

16.5 Pharmacokinetic Data

The PK Analysis Set will consist of all subjects who receive at least one dose of Avelumab, and provide at least one measurable post-dose concentration.

16.5.1 Descriptive PK Analysis

Avelumab concentrations in serum will be listed in tables and descriptively summarized by treatment, day and nominal time using the number of non-missing observations (N), number of missing observations (NMiss) arithmetic mean (Mean), standard deviation (StdDev), coefficient of variation (CV%), standard error of the mean (SEM), minimum (Min), median (Median) and maximum (Max). The pre-dose samples will be considered as if they had been taken simultaneously with the administration. Additional tables listing trough concentrations (Cmin) per cohort/day/administration will also be provided, and summarized descriptively using the aforementioned statistics.

For the calculation of descriptive statistics, values as presented in the data listings will be used. Concentrations will be set to missing in summary tables if the value is reported as N.R. (No result). PK concentrations below the lower limit of quantification (<LLOQ) are taken as zero for descriptive statistics. Minimum and maximum will be presented to the same decimal precision as collected. Mean, median and GeoMean will be presented to one decimal place more than the precision of the data collected. SD and SEM will be presented to two decimal places more than

the precision of the data collected. The coefficient of variation (CV%), GeoCV and the 95% CI will be reported to 1 decimal place.

Drug concentration in serum for HAHA ever-positive subjects versus HAHA never-positive subjects will be descriptively summarized to evaluate the potential effect of HAHA on pharmacokinetics.

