16.6 Human Anti-human Antibody (HAHA)

Subjects will be categorized as either never positive or ever positive (a positive result at any time point, including baseline). Listings of all individual HAHA results from ever positive subjects will be prepared by time point.

Subjects with a positive HAHA result prior to treatment with Avelumab will be characterized as pre-existing. If the titer increases ≥ 8 fold while on Avelumab treatment, they will be additionally characterized as treatment-boosted. The summary table will include the total pre-existing incidence as well as the treatment-boosted incidence.

Subjects not positive prior to treatment with Avelumab and with at least one positive result in the HAHA assay will be characterized as treatment-emergent and further characterized for persistence of antibody response. Subjects will be categorized as transient positive (time between first and last positive result < 16 weeks apart and a negative result at the most recent visit) or persistent positive (time between first and last positive result ≥ 16 weeks apart or a positive evaluation at the most recent visit). The summary table will include the total treatment-emergent incidence as well as the persistent and transient incidence. Table 6 below summarized the criteria of different HAHA result categories.

Table 6 Subjects Characterized based on HAHA Results

| Category | Definition | Subjects at Risk (Denominator for Incidence) |
|---------------------|---|---|
| Never positive | No positive results at any time point | Number of subjects with at least one valid result at any time point |
| Ever positive | At least one positive result at any time point | Number of subjects with at least one valid result at any timepoint |
| Pre-existing | A positive HAHA result prior to treatment with avelumab | Number of subjects with valid baseline result |
| Treatment boosted | A positive HAHA result prior to treatment with avelumab and the titer $\geq 8 \times$ baseline titer while on avelumab treatment | Number of subjects with valid baseline and at least one valid post-baseline result |
| Treatment emergent | Not positive prior to treatment with avelumab and with at least one positive post-baseline result | Number of subjects with at least one valid post-baseline result and without positive baseline results (including missing, NR) |

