| Trial Objectives | 
Primary objective
 
The primary objective of Part B of the trial is to evaluate the clinical activity of avelumab as first-line treatment for metastatic or distally recurrent MCC as determined by the durable response rate (DRR) according to RECIST 1.1 by an IERC.
 
Secondary objectives
 
Secondary objectives of Part B of the trial are as follows:
 
• To assess the OS time• To assess ORR according to RECIST 1.1• To assess DR according to RECIST 1.1• To assess PFS according to RECIST 1.1• To assess the safety profile of avelumab in subjects with MCC• To assess response status according to RECIST 1.1 at 6 and 12 months after start of study treatment• To characterize the population PK of avelumab in subjects with MCC by sparse sampling• To evaluate the immunogenicity of avelumab and to correlate it to exposure 
Exploratory objectives
 
CCI
  |
| Primary endpoint(s) | 
The primary endpoint of Part B of the trial is durable response, defined as objective response (CR or PR) according to RECIST 1.1, and as determined by an IERC, with a duration of at least 6 months.
 |

| | |
|--|--|
| 
Secondary/ Exploratory endpoints
 | 
Secondary endpoints of Part B of the trial include
 
• confirmed BOR per RECIST 1.1 as determined by an IERC,• DR according to RECIST 1.1 as determined by an IERC,• PFS time according to RECIST 1.1 as determined by an IERC,• occurrence and severity of treatment-related AEs according to NCI-CTCAE v 4.0,• OS time,• response status according to RECIST 1.1 at 6 and 12 months after start of study treatment,• serum titers of anti-avelumab antibodies, and• population PK profile of avelumab (sparse sampling). 
Exploratory endpoints of Part B of the trial include
 
CCI
  |

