16.5.1 Descriptive PK Analysis

Avelumab concentrations in serum will be listed in tables and descriptively summarized by treatment, day and nominal time using the number of non-missing observations (N), number of missing observations (NMiss) arithmetic mean (Mean), standard deviation (SD), coefficient of variation (CV%), standard error of the mean (SEM), minimum (Min), median (Median) and maximum (Max). The pre-dose samples will be considered as if they had been taken simultaneously with the administration. Additional tables listing trough concentrations (Cmin) per cohort/day/administration will also be provided, and summarized descriptively using the aforementioned statistics.

For the calculation of descriptive statistics, values as presented in the data listings will be used. Concentrations will be set to missing in summary tables if the value is reported as N.R. (No result). PK concentrations below the lower limit of quantification (<LLOQ) are taken as zero for descriptive statistics. Minimum and maximum will be presented to the same decimal precision as collected. Mean, median and GeoMean will be presented to one decimal place more than the precision of the data collected. SD and SEM will be presented to two decimal places more than the precision of the data collected. The coefficient of variation (CV%), GeoCV and the 95% CI will be reported to 1 decimal place.

Drug concentration in serum for ADA ever-positive subjects versus ADA never-positive subjects will be descriptively summarized to evaluate the potential effect of ADA on pharmacokinetics.

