17.5.3 Immunogenicity

ADA was assessed before the trial treatment start, and on Days 15, 29, 43, and 85 prior to the start of infusion, then every 6 weeks until Week 25, and every 12 weeks thereafter. ADA was also assessed at the End-of-Treatment and Safety Follow-up visits. If the sample is positive for ADA, it will be re-analyzed to determine the titer and nAb. The ADA results will be derived based on the algorithm in Table 9. Subjects will be characterized into different ADA categories based on the criteria in

Table 10.

Table 9 Algorithm for the Derivation of ADA Results

| Sample Screen Result | Confirmatory | Titer | ADA Result |
|----------------------|--------------|--------|--------------|
| Negative | NA | NA | Negative |
| NR | NA | NA | NR |
| Positive | Negative | NA | Negative |
| Positive | NR | NA | NR |
| Positive | Positive | Number | Number |
| Positive | Positive | NR | Positive-TNR |

NR = no result, NA = not applicable, TNR = titer no result.

Negative, number, or positive-TNR are valid results, while number and positive-TNR are considered as positive.

Table 10 Subjects Characterized based on ADA Results

| Category | Definition | Subject at Risk (Denominator for Incidence) |
|--------------------|--|---|
| Never positive | No positive results at any time point | Number of subjects with at least one valid result at any time point |
| Ever positive | At least one positive result at any time point | Number of subjects with at least one valid result at any time point |
| Pre-existing | A positive ADA result prior to treatment with avelumab | Number of subjects with valid baseline result |
| Treatment boosted | A positive ADA result prior to treatment with avelumab and the titer $\geq 8 \times$ baseline titer while on avelumab treatment | Number of subjects with valid baseline and at least one valid post-baseline result |
| Treatment emergent | Not positive prior to treatment with avelumab and with at least one positive post-baseline result | Number of subjects with at least one valid post-baseline result and without positive baseline results (including missing, NR) |
| Transient positive | If treatment emergent subjects have (a single positive evaluation, or duration between first and last positive result <16 weeks) and last assessment not positive. | Number of subjects with at least one valid post-baseline result and without positive baseline results (including missing, NR) |

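### The only antibody-PK comparison visible in the SAPs groups drug levels by ever- versus never-positive status, so samples taken before antibodies appeared or after they cleared count as positive and dilute any effect

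*SAP*

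**What the plan says.** Part A SAP, Section 16.5.1: "Drug concentration in serum for HAHA ever-positive subjects versus HAHA never-positive subjects will be descriptively summarized". The stated purpose is to see whether antibodies affect pharmacokinetics. Part B SAP, Section 16.5.1, has the same sentence with the newer term: "Drug concentration in serum for ADA ever-positive subjects versus ADA never-positive subjects will be descriptively summarized".

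Ever positive is defined per subject over the whole study. Part A, Section 16.6, describes it as "ever positive (a positive result at any time point, including baseline". Part B, Section 17.5.3, Table 10, has "At least one positive result at any time point".

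The general concentration tables in Section 16.5.1 are "descriptively summarized by treatment, day and nominal time". The ever/never sentence does not say whether it follows that layout.

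Both SAPs also define pre-existing, treatment-emergent, transient and persistent categories. Part A uses treatment-emergent versus everyone else for safety and PFS (Section 16.6). Part B lists the date of antibody onset for ever-positive subjects (Section 17.5.3). Neither SAP uses these categories or dates to group concentrations.

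The secondary objective behind this, in protocol Section 4 and in Section 6 of both SAPs, is: "To evaluate the immunogenicity of avelumab and to correlate it to exposure".

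**The concern.** An antibody can change drug levels only while it is present. A label earned at any time in the study is nevertheless attached to every concentration the subject contributes. Two groups of samples are misplaced by the SAPs' own definitions, whatever the onset pattern:

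- A treatment-emergent subject with a negative baseline result contributes Week 1 end-of-infusion samples to the positive group, although no antibody had been found when they were drawn.
- A transient positive must, by definition, be non-positive at the last assessment. Concentrations drawn after clearance still count as positive.

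If onset is not immediate, pre-onset troughs are misplaced in the same way. At stake is the reading of a stated secondary objective: a real fall in exposure after antibodies form would look smaller in this table than it is.

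**Working it through.** The plan gives no figure for this comparison, so there is none to reproduce. The check counts how many scheduled troughs precede onset and what that does to a ratio of means.

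**Inputs from the protocol (Sections 7.1.2.1, 7.1.2.2, 7.5, 7.6.3)**

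- Part A predose PK after the first dose, to Week 25: Weeks 3, 5, 7, 9, 11, 13, 15, 25 (8 troughs).
- Part B predose PK after the first dose, to Week 25: Weeks 3, 5, 7, 13, 19, 25 (6 troughs).
- Antibody samples after the first dose, both parts, to Week 25: Weeks 3, 5, 7, 13, 19, 25.

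**Assumptions, because the documents give no onset times, incidence or effect size**

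- First positive at one of the six antibody visits.
- Follow-up complete to Week 25, and no clearance.
- The effect starts at the first positive visit, with no other difference between the groups.
- True post-onset ratio to never-positive r = 0.50, varied from 0.30 to 0.80.

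**Formula.** With s the share of ever-positive troughs drawn before onset, the observed ratio is s + (1 − s) × r.

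**Pooled over visits, r = 0.50**

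| First positive | Part A: s | Part A: ratio | Part B: s | Part B: ratio |
|---|---|---|---|---|
| Week 3 | 0/8 | 0.50 | 0/6 | 0.50 |
| Week 5 | 1/8 | 0.56 | 1/6 | 0.58 |
| Week 7 | 2/8 | 0.63 | 2/6 | 0.67 |
| Week 13 | 5/8 | 0.81 | 3/6 | 0.75 |
| Week 19 | 7/8 | 0.94 | 4/6 | 0.83 |
| Week 25 | 7/8 | 0.94 | 5/6 | 0.92 |
| Even over the six | 22/48 = 0.458 | 0.73 | 15/36 = 0.417 | 0.71 |

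Example: Part A with even onset gives 0.458 + 0.542 × 0.50 = 0.73. Under even onset, a true 0.30 would read 0.62 (Part A) or 0.59 (Part B), and a true 0.80 would read 0.89 or 0.88.

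**By nominal visit, Part A, even onset, r = 0.50**

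| Visit | Not yet positive | Ratio |
|---|---|---|
| Week 3 | 5/6 | 0.92 |
| Week 5 | 4/6 | 0.83 |
| Weeks 7, 9, 11 | 3/6 | 0.75 |
| Weeks 13, 15 | 2/6 | 0.67 |
| Week 25 | 0/6 | 0.50 |

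Seven of the eight Part A troughs to Week 25 fall at or before Week 15.

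**A bias in the other direction.** If high drug levels hide antibodies from the assay, subjects with low exposure are more likely to test positive. An illustrative simulation assumed no causal effect, lognormal concentrations with a 60% coefficient of variation, and 10% of subjects forming antibodies. Detection probability was 1/(1 + c^b), where c is the concentration relative to its median. The ever/never ratio was 0.92, 0.85 and 0.75 for b = 0.5, 1 and 2. These inputs are assumptions and say nothing about the actual assay.

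**After the change below.** If samples are classed by status when drawn, s = 0 in the post-onset row, and the comparison with never-positive subjects at the same visit returns r under the assumptions above.

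**The case against.** - **Another analysis may carry this question.** Population PK is the primary PK analysis (protocol Section 8.5.3.3). Both SAPs (Section 16.5.2) use it to look for covariates and leave the details to a separate plan. Antibody status may be in that plan, and parts of the neighbouring SAP text are redacted. This stands. A reader might infer that the secondary objective is decided by the ever/never table alone. The documents show only that it is the one visible comparison.
- **Direction.** A reader might infer that the table must lean toward no effect. The documents do not support that for the net result. Protocol Section 8.5.3.4 plans an acid dissociation step so that antibodies can be found despite excess drug, which acknowledges the interference; any residue would act the other way. Subjects treated longer are also tested more often and have more chances to become ever positive. These are separate biases and do not remove the dilution.
- **Size.** It is hypothetical. Dilution is zero when antibodies are present at baseline or by the first post-dose trough. If the table is laid out by visit, equality before onset is correct and the full difference emerges later. This stands, but the sentence does not commit to that layout.
- **Listings.** Antibody results by time point (Part A), onset dates (Part B) and concentrations are listed anyway. With very few positives, listings may tell more than tables. Part A itself requires at least 5 positive subjects before it runs the safety and PFS subanalyses. That is a fair limit on what a finer table can show, but it does not justify the coarse one as the summary of effect.
- **Consequence.** The comparison is descriptive, with no test or decision attached. Part A SAP, Section 11, calls everything beyond the primary endpoint exploratory.

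**Conclusion.** The point holds in limited form. As written, the ever/never grouping places pre-onset concentrations, and those drawn after a transient positive has cleared, in the positive group. That dilutes any antibody effect on exposure. This follows from the SAPs' definitions.

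The amount is unknown. It ranges from nothing (onset by the first post-dose trough) to most of the effect (onset at Week 19 or later in Part A, where a true 0.50 would read 0.94 if pooled). Even onset gives about 0.73 in Part A and 0.71 in Part B. All of these figures rest on assumed onset times, an assumed halving of the trough and complete follow-up to Week 25.

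Neither the net direction of bias in the finished table nor the absence of an antibody term in the population PK model can be established from the documents. No primary endpoint is affected. Priority is low to moderate: the change is worth making because it is cheap and serves a stated secondary objective.

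**What to change.** In Section 16.5.1 of both SAPs:

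1. Summarize trough concentrations by nominal visit and by antibody status when the sample was drawn: never positive, before first positive, on or after first positive. Show pre-existing, transient and persistent subjects separately, so that samples from cleared transients are not mixed with those from persistent positives.
2. Where a trough has no paired antibody sample (Part A Weeks 9, 11 and 15), carry forward the most recent antibody result: Week 7 for Weeks 9 and 11, Week 13 for Week 15.
3. Show any within-subject change in trough from before to after onset only beside the change in never-positive subjects over the same visits. Early troughs may still be rising with repeated dosing, and an uncontrolled ratio could hide a fall.
4. Keep the ever/never table as supplementary, and state its layout.
5. Say whether the population PK plan includes antibody status and, if so, whether it varies with time.

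The cost is SAP wording and table programming on samples already scheduled. The downside is small cells when few subjects are positive; individual listings should then accompany the table. The regrouping does not correct for drug interference with the assay, which should be noted as a limitation.

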16.5.2 Population Pharmacokinetic Analysis

Sparse sampled PK profiles from study EMR 100070-003 will be analyzed jointly with data from CCI by non-linear mixed effect approach, in order to describe the PK concentration time profile followed by multiple dose infusion of avelumab, to identify covariates explaining (part of) the between patient PK variability and to estimate the residual PK inter-individual variability. More details will be given in a separate Data Analysis Plan for Population Pharmacokinetic Analysis. The results will be reported separately.

16.5.2.1 Relation of Pharmacokinetics to Efficacy

The exposure-response analysis will include the subjects of the ITT population from clinical trial 003 Part A as defined above for the primary analysis. The patients will be classified as responder or non-responder based on BOR according to RECIST 1.1 (responder: CR and PR; non-responder: stable disease [SD], progressive disease [PD], non-evaluable [NE]). The results will be reported separately.

CCI

The influence of the exposure parameter CCI on response will be explored graphically by depicting response (no/yes) versus exposure and applying a spline function to the data.

The relation between exposure and response will then assessed using logistic regression.

CCI

Based on this model, the probability of being responder will be depicted versus CCI. A 95% confidence interval will be added to the graph.

In a next step, covariates will be inserted in the logistic regression model.

CCI

Significance of covariates CCI [redacted] will be assessed using the Wald statistic ($\alpha=0.05$). All covariates will be inserted in the logistic regression model simultaneously and insignificant covariates will be eliminated one by one (starting with the most insignificant covariate) until all remaining covariates are significant.

The odds ratios with 95% confidence intervals for the significant covariates will be calculated and graphically presented in a Forest plot.

CCI

CCI

All exposure-response calculations will be done using the software program R or other software.

16.6 Human Anti-human Antibody (HAHA)

Subjects will be categorized as either never positive or ever positive (a positive result at any time point, including baseline). Listings of all individual HAHA results from ever positive subjects will be prepared by time point.

Subjects with a positive HAHA result prior to treatment with Avelumab will be characterized as pre-existing. If the titer increases ≥ 8 fold while on Avelumab treatment, they will be additionally characterized as treatment-boosted. The summary table will include the total pre-existing incidence as well as the treatment-boosted incidence.

Subjects not positive prior to treatment with Avelumab and with at least one positive result in the HAHA assay will be characterized as treatment-emergent and further characterized for persistence of antibody response. Subjects will be categorized as transient positive (time between first and last positive result < 16 weeks apart and a negative result at the most recent visit) or persistent positive (time between first and last positive result ≥ 16 weeks apart or a positive evaluation at the most recent visit). The summary table will include the total treatment-emergent incidence as well as the persistent and transient incidence. Table 6 below summarized the criteria of different HAHA result categories.

Table 6 Subjects Characterized based on HAHA Results

| Category | Definition | Subjects at Risk (Denominator for Incidence) |
|---------------------|---|---|
| Never positive | No positive results at any time point | Number of subjects with at least one valid result at any time point |
| Ever positive | At least one positive result at any time point | Number of subjects with at least one valid result at any timepoint |
| Pre-existing | A positive HAHA result prior to treatment with avelumab | Number of subjects with valid baseline result |
| Treatment boosted | A positive HAHA result prior to treatment with avelumab and the titer $\geq 8 \times$ baseline titer while on avelumab treatment | Number of subjects with valid baseline and at least one valid post-baseline result |
| Treatment emergent | Not positive prior to treatment with avelumab and with at least one positive post-baseline result | Number of subjects with at least one valid post-baseline result and without positive baseline results (including missing, NR) |
| Transient positive | If treatment emergent subjects have (a single positive evaluation, or duration between first and last positive result < 16 weeks) and last assessment not positive. | Number of subjects with at least one valid post-baseline result and without positive baseline results (including missing, NR) |
| Persistent positive | If treatment emergent subjects have duration between first and last positive result ≥ 16 weeks or a positive evaluation at the last assessment | Number of subjects with at least one valid post-baseline result and without positive baseline results (including missing, NR) |

If data permit (at least 5 ever positive or treatment emergent), subanalyses of immunogenicity responses on safety (TEAEs, TE irAEs, SAE, IRRs) and efficacy (PFS) will be performed using summary statistics for qualitative comparison only. This analysis will be conducted both by comparing ever positive versus never positive and by comparing treatment-emergent versus the rest of the subjects.

CCI

CCI

17 Safety Evaluation

Analysis sets: Safety analysis set

